2.6.3 Anticipated impact of the study on UK clinical practice

If [¹²⁴I]mIBG PET/CT is shown to be a significant advance on [¹²³I]mIBG scintigraphy this would have a major impact on current clinical practice in neuroblastoma in the UK and internationally. The potential clinical benefits of [¹²⁴I]mIBG PET/CT to neuroblastoma patients may be summarized as follows:

- It would offer increased sensitivity for predicting outcome and accurately stratifying therapy. Accurate disease staging is particularly critical, because of the very different therapies employed for the various risk groups. Failure to detect even very small disease foci, as currently occurs with [¹²³I]mIBG planar scintigraphy and 3D SPECT, even in expert hands, may lead to incorrect understaging, leading to insufficient first line therapy and early disease recurrence, with a major reduction in the chance of long term cure. Conversely, inappropriate overstaging leading to unnecessary treatment for high-risk disease may lead to growth reduction, thyroid function disorders, learning difficulties, and a greater risk of secondary cancers in these children.
- A major international strategy to improve the prognosis of high risk disease involves stratification of therapy based on response to indicial induction therapy based on response on [¹²³I]mIBG scintigraphy. The improved accuracy of [¹²⁴I]mIBG PET/CT would substantially strengthen this approach.
- It would replace the visual assessment of disease used in [¹²³I]mIBG scintigraphy with objective and reproducible quantitative measurement (SUV mean and max). Accurate quantitative assessment of disease extent would enable more rigorous and effective assessment of the efficacy of both existing and novel therapies.
- At least two investigations ([¹²³I]mIBG scintigraphy and CT scanning, and in some cases also bone scanning and MRI) would be replaced by one. This would speed up the diagnostic pathway and, as these scans often involve general anaesthetics in children, mean that only one rather than two (or more if other imaging techniques such as MRI are employed) general anaesthetics would be required.

3 STUDY DESIGN

3.1 CLINICAL STUDY OBJECTIVES AND ENDPOINTS

Primary objective	Endpoint
1. To show that [¹²⁴ I]mIBG PET/CT can detect an equal or greater number of neuroblastoma lesions compared to conventional [¹²³ I]mIBG planar scintigraphy.	1. Comparison of the percentage of lesions detected as positive by [¹²³ I]mIBG planar scintigraphy which are also considered positive with [¹²⁴ I]mIBG PET/CT.

Secondary objectives	Endpoints
1. To show that [¹²⁴ I]mIBG PET/CT can detect an equal or greater number of neuroblastoma lesions compared to conventional [¹²³ I]mIBG scintigraphy with 3D imaging by SPECT.	1. Comparison of the percentage of lesions detected as positive by [¹²³ I]mIBG SPECT which are also considered positive with [¹²⁴ I]mIBG PET/CT.
2. Assessing the safety and toxicity profile of a single intravenous administration of [¹²⁴ I]mIBG.	2. Determining the causality of each adverse event to [¹²⁴ I]mIBG and grading severity according to National Cancer Institute Common Toxicity Criteria for Adverse Events (NCI CTCAE) version 4.02.

Tertiary objectives	Endpoints
[REDACTED]	[REDACTED]
[REDACTED]	[REDACTED]
[REDACTED]	[REDACTED]
[REDACTED]	[REDACTED]
[REDACTED]	[REDACTED]
[REDACTED]	[REDACTED]
[REDACTED]	[REDACTED]
[REDACTED]	[REDACTED]
[REDACTED]	[REDACTED]
[REDACTED]	[REDACTED]

Tertiary objectives	Endpoints

[REDACTED]
 
[REDACTED]
 
[REDACTED]
 
[REDACTED]
 
[REDACTED]
 
[REDACTED]
 
[REDACTED]
 
[REDACTED]
	
[REDACTED]
 
[REDACTED]
 
[REDACTED]
 
[REDACTED]
 
[REDACTED]

[REDACTED]
 
[REDACTED]
 
[REDACTED]
 
[REDACTED]
	
[REDACTED]
 
[REDACTED]
 
[REDACTED]
 
[REDACTED]

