12 DATA ANALYSIS AND STATISTICAL CONSIDERATIONS

12.1 SAMPLE SIZE

The primary endpoint of the study is the percentage of lesions identified as positive using [¹²³I]mIBG planar scintigraphy which are also identified as positive on [¹²⁴I]mIBG PET/CT. The definition of a positive lesion is described in section 9.1. The aim is to prove that there is more than 90% agreement between the methods, with an expected level of agreement of 97%. Patients are expected to have a median of 3 lesions. Lesions are assumed to be independent within patients for the primary analysis. The following two stage design will be used, where the true proportion of agreement is denoted by P:

In the first stage, a total of at least 9 patients will be recruited, with a combined total of at least 50 lesions positive on [¹²³I]mIBG. Initially an exact one-sided binomial test of the null hypothesis: $P \geq 97\%$ will be done using $\alpha = 0.05$. If this is rejected in favour of the alternative hypothesis $P < 97\%$, the trial will be stopped early for futility. With a total of exactly 50 lesions this will occur if 45 or fewer lesions are also positive on [¹²⁴I]mIBG PET/CT.

If the null hypothesis is accepted, a further one-sided binomial test of the null hypothesis: $P \leq 90\%$ will be done using $\alpha = 0.025$. If this is rejected in favour of the alternative hypothesis $P > 90\%$ then the trial may be stopped early for efficacy. With a total of 50 lesions this will occur only if all 50 lesions are also positive in [¹²⁴I]mIBG PET/CT. If this null hypothesis is not rejected, the trial will continue to the second and final stage.

The second stage will end when an overall total of at least 33 patients with at least 100 lesions have been recruited. An exact one-sided binomial test of the null hypothesis: $P \leq 90\%$ will be done using $\alpha = 0.025$. If this is rejected in favour of the alternative hypothesis $P > 90\%$ then the trial will be declared a success. With a total of 100 lesions this will occur if at least 96 lesions are also positive on [¹²⁴I]mIBG PET/CT.

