12.2.1 Statistical Analysis of Primary Endpoint

The proportion of positive lesions detected by routine [¹²³I]mIBG planar scintigraphy which are also identified as positive using [¹²⁴I]mIBG PET/CT will be calculated. An exact one-sided binomial test of the null hypothesis that this proportion is not more than 90% will be performed, using an alpha of 0.025 to define significance.

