4.2 Analysis Methods

4.2.1 Primary endpoint

SIOPEN total numbers of lesions detected on [¹²⁴I]mIBG vs [¹²³I]mIBG will be compared as follows:

In the first stage, a total of at least 9 evaluable patients will be recruited, with a combined total of at least 50 lesions positive on [¹²⁴I]mIBG PET/CT. Initially an exact one-sided binomial test of the null hypothesis: $p \geq 97\%$ will be done using $\alpha = 0.05$. If this is rejected in favour of the alternative hypothesis $p < 97\%$, the study will be stopped early for futility.

If the null hypothesis is accepted, a further one-sided binomial test of the null hypothesis, $p \leq 90\%$ will be done using $\alpha = 0.025$. If this is rejected in favour of the alternative hypothesis $p > 90\%$ then the study may be stopped early for efficacy. If this null hypothesis is not rejected, the study will continue to the second and final stage.

Only if following the interim analysis recruitment is to continue, a second stage will be required and will end when an overall total of at least 33 evaluable patients with at least 100 lesions have been recruited. An exact one-sided binomial test of the null hypothesis, $p \leq 90\%$, will be done using $\alpha = 0.025$. If this is rejected in favour of the alternative hypothesis $p > 90\%$ then the study will be declared a success.

All above tests will be done using the following method: For each patient, the total number of lesions assessed as positive by consensus opinion (with confidence score 4 or 5) on [¹²³I]mIBG planar scintigraphy is referred to as n_{123} , and the total number of lesions assessed as positive by consensus opinion (with confidence score 4 or 5) on [¹²⁴I]mIBG PET/CT is referred to as n_{124} , with the minimum of these two numbers known as n_{\min} . The primary endpoint will be reported by the sum of n_{\min} over all patients, divided by the sum of n_{123} over all patients.

In addition, for each patient the difference and ratios between n_{123} and n_{124} will be calculated and the distribution of these variables will be summarised using the median, upper and lower quartiles. The number and percentage of patients with n_{124}/n_{123} less than 1, equal to 1 and greater than 1 will be reported.

Population to be used: Evaluable population & sensitivity population

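### Primary success shows that PET/CT finds more than 90% of planar-positive lesions; by itself it does not establish the stated objective of finding at least as many lesions

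*Combined protocol and SAP*

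**What the plan says.** **Objective.** Protocol 1.1 and 3.1, SAP 1.2 and the SAP addendum all state the same primary objective: to show that PET/CT "can detect an equal or greater number of neuroblastoma lesions compared to conventional" planar scintigraphy. This is a statement about counts.

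**Endpoint.** Beside it stands "Comparison of the percentage of lesions detected as positive by" planar scintigraphy that PET/CT also calls positive. The denominator is planar-positive lesions only.

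**Hypothesis.** Protocol 12.1 says: "The aim is to prove that there is more than 90% agreement between the methods, with an expected level of agreement of 97" per cent. Protocol 12.2.1 specifies a one-sided exact binomial test of 90% or less, "using an alpha of 0.025 to define significance". On the final success rule, 12.1 says: "With a total of 100 lesions this will occur if at least 96 lesions are also positive on" PET/CT.

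**Calculation.** SAP 4.2.1 does not match lesions one by one. For each patient it takes the smaller of n123 (planar-positive lesions) and n124 (PET/CT-positive lesions), sums these minima over patients and divides by the sum of n123.

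**Count comparison.** SAP 4.2.1 also summarises the per-patient differences and ratios by median and quartiles. It adds: "The number and percentage of patients with" n124/n123 below, at or above 1. No test or claim criterion is attached.

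**Addendum.** It repeats the objective and endpoint, moves the analysis to skeletal segments, and adds sensitivity and specificity against a combined consensus read. It sets no success criterion for these.

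**The concern.** The objective asks whether PET/CT finds at least as many lesions. The test asks whether PET/CT reproduces more than nine tenths of what planar scintigraphy found. A proportion capped at 100% cannot show a greater number, and a null of 90% does not test for an equal one. In effect the test is a non-inferiority comparison with a 10-point margin, placed under an objective that has no margin.

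The consequence lies in what a positive result may be said to show. Protocol 2.6 and 2.6.3 rest the case for PET/CT on higher sensitivity and on the harm of missing small disease foci. If success were reported in the words of the objective, the claim would go beyond the evidence. The figures that do bear on counts, n124 and n123, carry no interval and no rule in SAP 4.2.1.

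**Working it through.** **1. Reproduce the design.** Inputs from Protocol 12.1: 50 lesions at stage 1; stop for futility at 45 or fewer; stop for efficacy at 50; otherwise continue to 100 lesions and succeed at 96 or more. Lesions are taken as independent, as the plan assumes.

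Pr(success | P) = P^50 + Σ (x = 46 to 49) Pr(X₁ = x) · Pr(X₂ ≥ 96 − x), with X₁ and X₂ each binomial(50, P).

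| Quantity | Plan | Recomputed |
|---|---|---|
| Power at 97% | 82% | 0.8215 |
| Alpha at 90% | 0.03 | 0.0266 |
| Early efficacy stop at 97% | 22% | 0.218 |
| Early futility stop at 90% | 57% | 0.569 |

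The stated figures reproduce.

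**2. What success shows.** Pr(X ≥ 96 | 100, 0.90) = 0.0237 and Pr(X ≥ 95) = 0.0576, so 96 is the cut. The exact one-sided 97.5% lower bound at 96/100 is the 0.025 quantile of Beta(96, 5), which is 90.07%. At 50/50 it is 0.025^(1/50) = 92.9%. A success at the final cut is therefore compatible with nearly 10% of planar-positive lesions being missed.

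**3. Does the result follow the counts?** Three constructed data sets follow, each with 33 patients having 3 planar lesions and one patient having 1 (33 × 3 + 1 = 100). They illustrate the rule and are not predictions.

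| Case | PET/CT findings | Sum n124 | Sum of minima | p against 90% | Result |
|---|---|---|---|---|---|
| A | 3 in 29 patients, 2 in four, 1 in the last | 87 + 8 + 1 = 96 | 96 | 0.0237 | Success |
| B | 6 in 28 patients, 2 in five, 1 in the last | 168 + 10 + 1 = 179 | 84 + 10 + 1 = 95 | 0.0576 | Not a success |
| C | In each of 33 patients, one planar lesion missed and one other lesion found | 100 | 100 | below 0.001 | Success |

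A succeeds with fewer lesions in total. B, if it reaches the final analysis, fails with 79% more. In C the SAP ratio is 100/100, although lesion-by-lesion agreement is 100 − 33 = 67 of 100.

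**4. How often this could happen.** With true agreement of 95%, 96% or 97%, the formula in step 1 gives success probabilities of 0.44, 0.64 and 0.82. If PET/CT found nothing beyond the planar lesions, it would truly find fewer lesions in each case. At 97%, 0.603 of the 0.822 success probability (73%) comes through stage 2, which is reached only after at least one shortfall.

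**5. Would requiring a lower limit of at least 1 on the count ratio test the objective?** Assumed inputs: 33 patients, about 3 planar lesions each, 97% detected by PET/CT, and PET-only lesions equal to 3% of the planar count, so that true totals are equal. In simulation, a patient-resampled 95% interval for sum(n124)/sum(n123) had a lower limit of at least 1 in only about 6% to 8% of trials. With PET-only lesions at 10% of the planar count, the rate was about 61% to 63%. The rule is in effect a superiority test. It would usually fail if the counts were truly equal.

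**The case against.** The plan does not hide what it tests: Protocol 12.1 and 12.2.1 and SAP 1.4 all state the 90% hypothesis, and a 90% bound is a legitimate margin. This stands, and it is why the bound and the decision rule can stay. It does not reconcile the hypothesis with the objective, which the addendum repeats unchanged.

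Three stronger readings are tempting, and the documents do not support them.

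- A reader might infer that PET-only lesions never count. That fits the protocol's endpoint wording, but not the SAP calculation. There, a PET-only lesion enters n124 and can offset a missed planar lesion in the same patient (case C). Only the surplus above the planar count is lost. For the same reason, 96/100 under the SAP means a within-patient count shortfall of 4, not necessarily four missed lesions.
- A reader might infer that success can never support the objective. An early stop at 50/50 means that n124 is at least n123 in every patient in the sample, which is real, though partial, support.
- A reader might infer that the sponsor will report success as a count claim. No section fixes that wording; the risk comes from leaving the objective as it is.

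Other provisions also bear on the question. SAP 4.1 plans summary measures of agreement between modalities with 95% confidence intervals unless specified otherwise. The addendum's sensitivity analysis would credit PET-only lesions accepted in the combined read. Neither sets a criterion for the count objective. The tertiary analyses are redacted, so nothing can be said about them.

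**Conclusion.** The mismatch holds. Primary success establishes that PET/CT detects more than 90% of planar-positive lesions; alone, it does not establish that PET/CT detects at least as many lesions as planar scintigraphy. At the final cut the bound is 90.07%. The decision can go against the counts in both directions (96 against 100 succeeds, 179 against 100 fails). If PET/CT truly reproduced 95% of planar lesions and found nothing else, success would still have probability 0.44.

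No stated design figure is wrong on this point; what needs correcting is what success may be said to show. The probabilities rest on the plan's independence assumption and on totals of exactly 50 and 100 lesions. The three cases and the simulation rest on the assumed inputs shown. The secondary SPECT objective pairs the same kind of count statement with a 90% null (Protocol 12.2.2, SAP 4.2.2), so the same limit applies there.

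**What to change.** 1. State in the protocol and SAP that primary success supports only the conclusion that PET/CT detects more than 90% of planar-positive lesions, and that it will not be reported as showing an equal or larger count. Keep the 90% bound and the decision rule. Word the SPECT conclusion in the same way.
2. Report sum(n124)/sum(n123) with a 95% interval from resampling patients, as the estimate that addresses the count objective. Say that it applies to patients with at least one planar-positive lesion, since the Evaluable Population requires one.
3. Require a lower limit of at least 1 only for a claim that PET/CT detects more lesions.
4. State whether the endpoint is lesion-matched, as the protocol wording implies, or based on the per-patient minimum, as in SAP 4.2.1.

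The cost is a narrower headline claim and one extra analysis of per-patient counts that are already collected. No scans, patients or thresholds change. Two limits should be stated. If the trial stops with as few as 9 patients, a resampled interval will be rough. And because the addendum followed review of a statistical report, the ratio should be labelled as added after that review.

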3.2 PATIENT EVALUABILITY

To be evaluable for the primary imaging analysis a patient must be eligible for the study, receive [¹²³I]mIBG and undergo planar scintigraphy, fulfil the clinical criteria for [¹²⁴I]mIBG imaging, receive [¹²⁴I]mIBG and complete the required PET/CT scanning schedule in accordance with the Study Imaging Manual. Any patient who is not evaluable for the primary imaging analysis will be replaced.

To be evaluable for the assessment of toxicity a patient must have received [¹²⁴I]mIBG.

3.3 DESIGN OF THE CLINICAL STUDY

This is a multi-centre, non-therapeutic Phase I/II study directly comparing [¹²⁴I]mIBG PET/CT and conventional [¹²³I]mIBG imaging in patients with newly diagnosed, relapsed or refractory metastatic neuroblastoma. A minimum of 9 (if stopped after interim analysis) or 33 evaluable patients will be scanned at two centres in the UK.

Patients will be those who require routine [¹²³I]mIBG planar scintigraphy as a means of assessing response to their ongoing treatment or for staging of their disease. The majority of patients will also be planned to undergo 3D imaging by SPECT where this is available. Eligible patients will undergo the planned routine [¹²³I]mIBG imaging as part of this study. These routine [¹²³I]mIBG planar scintigraphy findings will be reported by a Nuclear Medicine physician at the investigational site and will be used to confirm suitability for the subsequent novel [¹²⁴I]mIBG PET/CT imaging prior to administration of the novel [¹²⁴I]mIBG Solution for Injection.

Please refer to section 7.9 Schedule of Assessments for a detailed table of the relative timing of the study scans. The [¹²⁴I]mIBG PET/CT imaging will take place approximately 3-21 days after routine [¹²³I]mIBG imaging and before the commencement of any new anti-cancer therapy. Patients who fulfil the clinical criteria for [¹²⁴I]mIBG imaging in Section 4.1.3 will receive one injection of [¹²⁴I]mIBG and undergo imaging with [¹²⁴I]mIBG PET/CT the following day. Patients who do not fulfil these criteria will be withdrawn from the study. [¹²⁴I]mIBG PET/CT imaging undertaken as part of the clinical study will not affect the management or delay the treatment of patients recruited to this study.

[¹²⁴I]mIBG PET/CT imaging data from the first patient will be analysed immediately by the Investigators to assess whether the scanning equipment specifications and scanning methodology are effective. The methodology will be adapted as required to ensure the quality of subsequent imaging data. Adaptations may also be made to resolve any practical and logistical issues with the events schedule for the next patient. Recruitment to the study will be competitive between centres. There is no minimum time interval required between patients.

The interim analysis will be performed after a minimum of 50 lesions have been identified by [¹²³I]mIBG planar scintigraphy from a minimum of 9 evaluable patients. If the number of lesions which

CONFIDENTIAL

were also identified using [¹²⁴I]mIBG PET/CT is less than 45 out of 50 the trial will be stopped early for futility. If all lesions (e.g. 50 out of 50) were also identified using [¹²⁴I]mIBG PET/CT the trial may be stopped early for efficacy. Otherwise recruitment will continue until a minimum of 100 lesions have been identified by [¹²³I]mIBG planar scintigraphy from a minimum of 33 evaluable patients.

The imaging review will be performed separately by an agreed number of observers who are Nuclear Medicine physicians experienced in the assessment of neuroblastoma. Two observers will be study Investigators and all others will be independent from the study to prevent subjective bias in the interpretation of the nuclear medicine mIBG scans. Lesions will be identified and scored by each observer using a diagnostic confidence level. The observers will review the lesions identified and where there is a difference in their separate scores they will return to the imaging in order to reach a consensus score. The number of lesions identified as positive by this scoring will be used to meet the primary objective of comparison of the novel [¹²⁴I]mIBG PET/CT modality with the recommended standard mIBG imaging modality for neuroblastoma which is [¹²³I]mIBG planar scintigraphy (see Section 9.1).

The majority of patients treated for neuroblastoma will have [¹²³I]mIBG scintigraphy using 3D SPECT over the chest and abdomen in addition to planar scintigraphy of the full body. The imaging review performed for the assessment of the primary objective will be repeated to read and score lesions identified by the available [¹²³I]mIBG SPECT. The number of positive lesions identified by SPECT will be used to meet the secondary objective of comparison of [¹²⁴I]mIBG PET/CT with [¹²³I]mIBG scintigraphy with 3D SPECT.

[REDACTED]

All patients will be monitored for safety reporting from the time the patient / parent or guardian (as applicable) provides informed consent until the Off-Study assessment on Day 3 (the day after the [¹²⁴I]mIBG PET/CT scan) to Day 7. The Off-Study assessment should either take place during a routine clinic visit or by telephone prior to the start of subsequent anti-cancer therapy. If there are any reported events considered to be related (highly probably, probably or possibly) to [¹²³I]mIBG and/or [¹²⁴I]mIBG which are still present at the Off-Study assessment, the patient will be followed by their Paediatric Oncologist until resolution, recovery to baseline, or stabilisation of these events, unless the patient starts another anti-cancer therapy.

3.3.1 [REDACTED]

[REDACTED]

3.3.2 [REDACTED]

[REDACTED]

4 PATIENT SELECTION

4.1 ELIGIBILITY CRITERIA

The patient must fulfil the eligibility criteria presented in Sections 4.1.1 and 4.1.2 prior to enrolment on the clinical trial and the subsequent administration of [¹²³I]mIBG. [REDACTED]

Following [¹²³I]mIBG planar scintigraphy ± SPECT for routine clinical care of neuroblastoma, patients will only continue in the study and undergo [¹²⁴I]mIBG imaging if they fulfil the additional clinical criteria outlined in Section 4.1.3.

4.1.1 Inclusion Criteria

1. Histologically proven neuroblastoma with stage 4 disease as defined by the International Neuroblastoma Staging System (INSS)
2. Aged ≥ 1 year at the time that written informed consent is given.
3. Planned to undergo conventional [¹²³I]mIBG planar scintigraphy for routine clinical care of neuroblastoma.
4. Life expectancy of at least 12 weeks.
5. World Health Organisation (WHO) performance status of 0, 1 or 2 (Appendix 2) for patients aged > 12 years old or Lansky play scale score of ≥ 50% (Appendix 3) for patients aged ≤ 12 years old.
6. Written (signed and dated) informed consent from patient ≥ 16 years old and/or parent or legal guardian for patients <16 years old and the patient be capable of co-operating with scanning requirements. (N.B. Written or verbal assent as appropriate should be sought from all patients who are under 16 years old).

4.1.1.1 [REDACTED]

- [REDACTED]
- [REDACTED]

4.1.1.2 [REDACTED]

- [REDACTED]
- [REDACTED]
- [REDACTED]

